8.2.2.2. Treatment-Emergent Marked Laboratory Abnormalities

Treatment-emergent marked laboratory abnormalities during the double-blind phase are defined as values that increase from baseline by at least 3 toxicity grades at any postbaseline time point, during double-blind phase. Treatment-emergent marked laboratory abnormalities during the extension phase are defined as values that increase from baseline by at least 3 toxicity grades at any postbaseline time point during extension phase.

If the relevant baseline laboratory value is missing, any Grade 3 or 4 values observed within the timeframe specified above will be considered treatment-emergent marked abnormalities.

8.2.2.3. Summaries of Laboratory Abnormalities

The following summaries (number and percentage of subjects) for treatment-emergent laboratory abnormalities will be provided by lab test and treatment (double-blind treatment for double-blind phase; treatment sequence for extension phase). Subjects will be categorized according to the most severe postbaseline abnormality grade for a given lab test:

- Graded laboratory abnormalities (for the final analysis of the study only)
- Grade 3 or 4 laboratory abnormalities
- Marked laboratory abnormalities

For all double-blind phase summaries of laboratory abnormalities, the denominator is the number of subjects with ≥ 1 nonmissing postbaseline value during the double-blind phase. For the extension phase the denominator is the number of subjects with ≥ 1 nonmissing postbaseline value during the extension phase.

A by-subject listing of treatment-emergent Grade 3 or 4 laboratory abnormalities will be provided by subject ID number and time point in chronological order. This listing will include all test results that were collected throughout the study for the lab test of interest, with all applicable severity grades displayed.

8.2.3. Liver-related Laboratory Evaluations

Liver-related abnormalities will be examined and summarized (by double-blind treatment during double-blind phase; by treatment sequence during extension phase) using the number and percentage of subjects with ≥ 1 value in the reporting period for the following:

- AST: (a) > 3 times the upper limit of normal range (ULN); (b) $> 5 \times$ ULN; (c) $> 10 \times$ ULN; (d) $> 20 \times$ ULN
- ALT: (a) $> 3 \times$ ULN; (b) $> 5 \times$ ULN; (c) $> 10 \times$ ULN; (d) $> 20 \times$ ULN
- (AST or ALT $> 3 \times$ ULN) and (total bilirubin $> 2 \times$ ULN)

For individual laboratory tests, subjects will be counted once based on their most severe postbaseline value during the double-blind phase for double-blind phase summaries and most severe postbaseline value during the extension phase for extension phase summaries. For the composite endpoint of AST or ALT and total bilirubin, subjects will be counted once when the criteria are met at the same postbaseline visit date. The denominator is the number of subjects in the Safety Analysis Set who have ≥ 1 nonmissing postbaseline value of all relevant tests at the same postbaseline visit date for visits during double-blind phase; and the number of subjects with ≥ 1 nonmissing postbaseline value of all relevant tests at the same post baseline visit date for visits during the extension phase for the Extension Phase Safety Analysis Set.

A listing of subjects who met at least 1 of the above criteria will be provided.

8.3. Body Weight and Vital Signs

Descriptive statistics will be provided by treatment (double-blind treatment for double-blind phase; treatment sequence for extension phase) for body weight, BMI and vital signs (pulse, systolic and diastolic blood pressure, respiration rate, and temperature) as follows:

- Baseline value
- Values at each postbaseline time point
- Change from baseline at each postbaseline time point

A baseline value will be defined as the last available value collected on or prior to the date of first dose of study drug. Change from baseline to a postbaseline visit will be defined as the postbaseline value minus the baseline value.

In the case of multiple values in an analysis window, data will be selected for analysis as described in Section 3.7.3. No formal statistical testing is planned.

A by-subject listing of vital signs will be provided by subject ID number and time point in chronological order. Body weight, height, and BMI will be included in the vital signs listing, if space permits. If not, they will be provided separately.

8.4. Prior and Concomitant Medications

Medications collected at screening and during the study will be coded using the current version of the WHO Drug dictionary.

8.4.1. Prior Medications

Prior medications are defined as any medications taken before a subject took their first dose of study drug.

If a partial start date is entered, the medication will be considered prior unless the month and year (if day is missing) or year (if day and month are missing) of the start date are after the first dosing/start date in the relevant phase of the study. Medications with a completely missing start date will be assumed to be a prior medication, unless otherwise specified.

Prior medications will be listed as part of the Prior and Concomitant Medications listing.

8.4.2. Concomitant Medications

Concomitant medications are defined as medications taken while a subject is also taking study drug. Use of concomitant medications will be summarized by ATC preferred name using the number and percentage of subjects for each treatment group. A subject reporting the same medication more than once will be counted only once when calculating the number and percentage of subjects who received that medication. The summary will be provided by preferred term in descending overall frequency. For drugs with the same frequency, sorting will be done alphabetically.

For the purposes of analysis, any medications with a start date prior to or on the first dosing date of study drug that are continued after the first dosing date or started after the first dosing date but prior to or on the last dosing date of study drug will be considered concomitant medications. Medications started and stopped on the same day as the first dosing date or the last dosing date of study drug will also be considered concomitant. Medications with a stop date prior to the date of first dosing date of study drug or a start date after the last dosing date of study drug will be excluded from the concomitant medication summary. If a partial stop date is entered, any medication with the month and year (if day is missing) or year (if day and month are missing)

prior to the date of first study drug administration will be excluded from the concomitant medication summary. If a partial start date is entered, any medication with the month and year (if day is missing) or year (if day and month are missing) after the study drug stop date will be excluded from the concomitant medication summary. Medications with completely missing start and stop dates will be included in the concomitant medication summary, unless otherwise specified (ie, the medication is specifically marked as a prior medication on the eCRF).

Summaries during the double-blind phase will be by double-blind treatment group for subjects in the Safety Analysis Set. Summaries during the extension phase will be by treatment sequence for subjects in the Extension Phase Safety Analysis Set.

No formal statistical testing is planned.

All prior and concomitant medications (other than per-protocol study drugs) will be provided in a by-subject listing sorted by subject ID number and administration date in chronological order.

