Study Drug	Study drug is defined as blinded filgotinib or placebo during the Double-blind Treatment Phase and open-label filgotinib during the Extension Phase.
First unblinded interim analysis (IA1)	Unblinded Week 26 analysis to be performed after at least 200 evaluable subjects pooled across studies GS-US-418-4279 (GLPG0634-CL-228) and GLPG0634-CL-227 complete Week 13 and evaluable subjects from Study GLPG0634-CL-227 complete Week 26 or permanently discontinue from study drug. Referred to as 'Week 26 Analysis' in the SAP.
Second unblinded interim analysis (IA2)	Unblinded Week 26 analysis to be performed after all subjects reach Week 26 and all subjects with a $\geq 50\%$ decrease in sperm concentration, and/or motility, and/or morphology up to Week 26 enter the Monitoring Phase and either meet reversibility criteria or are followed off-treatment for 52 weeks, whichever occurs first. Referred to as 'Week 26 and Reversibility Analysis for Pre-specified Sperm Decreases Up to Week 26' in the SAP.

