### 3.1. Double-blind Treatment Phase (Day 1 through Week 13 Study Visit)

Figure 3-2. Double-blind Treatment Phase – Week 13 Evaluation

[figure not shown]

During the Double-blind Treatment Phase, all subjects will receive blinded study drug for 13 weeks starting from the Day 1/Randomization Study Visit. Subjects will visit the clinical study center to be evaluated for clinical and laboratory assessments at Day 1, Week 2, Week 4, Week 8, and Week 13. At the Week 13 study visit, sperm parameters (see Semen collection and Analysis) will be evaluated to determine whether they meet any of the pre-specified decrease thresholds (see [Definition of Terms](#)). In addition, arthritis response status (Arthritis Non-responder vs Arthritis Responder, see [Definition of Terms](#)) will be determined. As soon as the Week 13 semen results are available to the investigator and have been evaluated, subjects are assigned to one of the following:

- Subjects whose semen parameters meet any of the pre-specified decrease thresholds, regardless of arthritis response status, will discontinue blinded study drug and enter the Monitoring Phase. These subjects will also have a safety follow-up visit 30 days after last study drug dose.
- Subjects who are arthritis Non-responders and whose sperm parameters do not meet any of the pre-specified decrease thresholds will discontinue blinded study drug and start Standard of Care treatment (see [Definition of Terms](#)) during the Extension Phase. These subjects will also have a safety follow-up visit 30 days after last study drug dose.
- Subjects who are Arthritis Responders and whose sperm parameters do not meet any of the pre-specified decrease thresholds will be unblinded by the IWRS system and enter the Extension Phase. Subjects on filgotinib will convert to open-label filgotinib and subjects receiving placebo will switch to Standard of Care treatment.

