3.7. Analysis Visit Windows

3.7.1. Definition of Study Day

The First Dosing Date of Double-Blind Filgotinib/Placebo is defined as the date when subjects take their first dose of double-blind filgotinib/placebo as recorded on the Study Drug Administration eCRF.

The Last Dosing Date of Double-Blind Filgotinib/Placebo is defined as the date when subjects take their last dose of double-blind filgotinib/placebo as recorded in the Study Drug Administration eCRF.

The Last Dosing Date of Any Filgotinib is defined as the date when a subject takes their last dose of double-blind or open-label filgotinib as recorded in the Study Drug Administration eCRF.

The Start Date of Extension Phase is defined as the first dose date of open-label filgotinib (for rheumatic disease responders randomized to filgotinib who continued on open-label filgotinib in extension phase) from the study drug administration eCRF or last dose date of double-blind study drug +1 day for subjects who have a non-missing standard of care start date in the extension phase of the study. In some countries, it takes time to obtain a new standard of care drug for rheumatic disease when subjects undergo a medication switch (especially for biologics), so the “standard of care” is to continue background medications alone or in rare cases, to take no rheumatic disease medication until the new regimen is available.

The End Date of Extension Phase is defined as last dose date of open-label filgotinib as recorded on the Study Drug Administration eCRF for subjects on open-label filgotinib in the Extension Phase. The end date for standard of care in extension phase will be 1 day prior to the date the subject went into the Monitoring Phase (ie, date the site was notified of subject meeting a prespecified sperm decrease threshold). Subjects who do not participate in Monitoring Phase but have a Study Completion eCRF that states that the subject has either completed study or prematurely discontinued study will have the last date of standard of care estimated using the last of the following dates: last Covance lab date, last eCRF visit date, date of last sperm sample collection, and death date (if subject died).

Study Day will be calculated from the first dosing date of double-blind filgotinib/placebo and derived as follows:

- For postdose study days: Assessment Date – On-Filgotinib/Placebo Study Day 1 + 1
- For days prior to the first dose: Assessment Date – On-Filgotinib/Placebo Study Day 1

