Follow-up (FU) Day will be calculated from last study drug (double-blind study drug or open-label filgotinib) dosing date or end date of extension phase for subjects on standard of care.

The FU day is derived as Assessment Date – Last Dose Date of study drug/end date of extension phase for subjects on standard of care

Therefore, Follow-up Day 1 is the first day after permanent discontinuation of all study drugs or end of Extension Phase for subjects on standard of care in extension phase.

Baseline is defined as the last available observation taken on or prior to the first dose date of double-blind filgotinib/placebo study drug.

For semen parameters, including sperm concentration, total sperm count, ejaculate volume, sperm total motility, and sperm morphology, the baseline value is the mean of 2 evaluable samples from the screening visit. The baseline value for sperm parameters is used to determine whether subjects have met a sperm parameter decrease threshold (ie, $\geq 50\%$ decrease from baseline in sperm concentration and/or motility and/or morphology).

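### SAP 8.4.2 drops medicines newly started in the extension for both standard-of-care sequences but counts them for open-label filgotinib

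*SAP*

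**What the plan says.** SAP 8.4.2 opens with the definition: "Concomitant medications are defined as medications taken while a subject is also taking study drug". It then sets date rules. A medicine is left out of the summary if it stopped before the first study-drug dose. It is also left out if it has "a start date after the last dosing date of study drug will be excluded from the concomitant medication summary". For the output, the section states: "Summaries during the extension phase will be by treatment sequence for subjects in the Extension Phase Safety Analysis Set". It gives no separate dates for that phase.

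The Protocol (Definition of Terms) fixes the key term: "Study drug is defined as blinded filgotinib or placebo during the Double-blind Treatment Phase and open-label filgotinib during the Extension Phase". SAP 3.7.1 also keeps standard of care apart from study drug. It counts follow-up days from the "last study drug (double-blind study drug or open-label filgotinib) dosing date or end date of extension phase for subjects on standard of care". For men on standard of care, the same section sets the extension start at the "last dose date of double-blind study drug +1 day for subjects who have a non-missing standard of care start date in the extension phase". Protocol 3.1 gives the same order of events for non-responders, who "will discontinue blinded study drug and start Standard of Care treatment".

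SAP 3.2 names three extension sequences, two of which end in standard of care.

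**The concern.** From Week 26 on, semen, hormone and safety results are displayed by treatment sequence (by sequence and responder status for semen and hormones at Week 26). A reader who compares the sequences will want to know what the standard-of-care men were taking. Background treatment and standard of care may be changed during the extension (Protocol 3.2), and randomization was stratified by methotrexate use because of its possible effect on spermatogenesis (Protocol 1.3).

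The omitted medicines are also the ones that differ most from baseline treatment. Protocol Table 5-1 bars TNF antagonists, interleukin antagonists, other JAK inhibitors and several other DMARDs until the double-blind phase ends, and beyond that only for men on open-label filgotinib. A protocol-compliant man on standard of care who uses one of these would ordinarily have started it after his last blinded dose, so the rule removes it.

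There is a possible knock-on effect. SAP 8.1.6 plans extension-phase tables of treatment-emergent AEs and SAEs split by use of immunomodulators and corticosteroids, and the SAP text seen here gives no other definition of use. If 8.4.2 supplies it, a man on standard of care who starts such a drug in the extension is classed as a non-user, while a man on open-label filgotinib who does the same is classed as a user.

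**Working it through.** The plan states no figure on this point, so there is nothing to reproduce. The check applies the written rule to example dates.

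**Inputs**
- Rule (SAP 8.4.2): a medicine is counted unless its stop date < F or its start date > L, where F and L are the first and last study-drug dosing dates.
- Study drug excludes standard of care (Protocol, Definition of Terms; SAP 3.7.1).
- Extension start for standard-of-care men = last double-blind dose + 1 day (SAP 3.7.1).
- Assumed dates: F = Day 1; last double-blind dose = Day 92 (the SAP's nominal Week 13 day); last open-label dose, and end of extension, = Day 1092 (Week 156 in SAP 4.2.1).

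**Step 1: the last study-drug date L.** For both standard-of-care sequences L = 92. For filgotinib to open-label filgotinib L = 1092.

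**Step 2: the general result.** For standard-of-care men the extension starts on Day 92 + 1 = 93. Any medicine started in the extension has a start date ≥ 93 > 92 = L and is excluded. This does not depend on Day 92, because the extension start is defined as L + 1.

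**Step 3: examples.** The last column applies an extension window instead, counting a medicine in any sequence if it overlaps Day 93 to Day 1092.

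| Medicine | 8.4.2, both standard-of-care sequences | 8.4.2, open-label sequence | Extension window, all sequences |
|---|---|---|---|
| Background methotrexate, started before Day 1, continued | counted | counted | counted |
| Started on Day 92, continued | counted | counted | counted |
| Started on Day 93, continued | excluded | counted | counted |
| Started on Day 120, continued | excluded | counted | counted |
| Taken from Day 400 to Day 430 | excluded | counted | counted |
| Background methotrexate stopped on Day 80 | counted | counted | not counted |

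Rows three to five show the asymmetry. The last row shows that the date rule also lets in a medicine that ended before the extension began.

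**Step 4: length of the gap.** (1092 − 92) / 7 = 142.9 weeks for a man followed to Week 156, in line with the extension of up to 143 weeks in Protocol 3.6.

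**Step 5: the double-blind table.** Under the same literal rule, a medicine started on Day 400 by a man on open-label filgotinib has start date 400 ≤ 1092 = L. It therefore meets the definition for the double-blind summary too. With a window from Day 1 to Day 92 it does not. Both summaries need their own dates.

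**The case against.** The strongest reply is that phase-specific dates were intended. Section 8.4.2 asks for separate double-blind and extension summaries. The Extension Phase Safety Analysis Set (SAP 3.1.3) is defined by taking open-label filgotinib or standard of care. SAP 8 and 8.2.2.1 treat standard of care as the extension treatment, and the partial-date rule in SAP 8.4.1 refers to the relevant phase. Because the literal rule also spoils the double-blind table, a programmer might well apply each phase's own dates.

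That intention is plausible, but 8.4.2 does not state it. Men on standard of care have no study-drug dosing dates in the extension, so restricting the rule to that phase leaves it without dates to use. The relevant-phase wording belongs only to prior medications with partial dates. Where other sections need a standard-of-care date, they say so explicitly; 8.4.2 does not.

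A second reply is that the data are not lost. Protocol 5.3 records all medicines to the end of participation, SAP 3.7.1 relies on a recorded standard-of-care start date, and 8.4.2 plans a by-subject listing. This stands in part. The exclusion clauses mention only the summary, so the listing may be complete. But it is described as covering prior and concomitant medicines, the same restricted term, and a listing is not a summary by sequence.

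A reader might go further and infer that the table shows no standard of care at all, or that every man in the two sequences is affected. The documents do not support that. SAP 3.7.1 explains that in some countries standard of care means continuing background medicines alone, or rarely taking none, until a new regimen arrives; continued background medicines pass the rule. So does a partial start date in the same month as the last dose. The rule applies to every such man, but the documents do not say how many start something new.

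**Conclusion.** The point holds for newly started medicines. As written, the extension summary omits them for two of three sequences, for up to about 143 weeks, and counts them for the third. The misclassification in the SAP 8.1.6 tables is conditional on 8.4.2 being the definition used there.

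The consequence is limited to descriptive output. A reader might infer that the extension semen results cannot be interpreted, or that the trial's main findings are affected; neither follows. The displays at Week 26 and later (SAP 6.5.1 and 6.5.2) are descriptive and do not draw on this table, and no primary or secondary endpoint estimate changes. This is a minor but real defect in a stated rule.

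The conclusion rests on the Protocol's definition of study drug applying in 8.4.2. No other table of standard-of-care medicines appears in the SAP text seen here. Parts of SAP sections 3.1, 4.1 and 6 were not available, so such a table cannot be fully ruled out.

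**What to change.** Give SAP 8.4.2 a window for each phase:
- Double-blind summary: count medicines that overlap the first to last double-blind dosing dates.
- Extension summary: count medicines that overlap the extension start and end dates of SAP 3.7.1, in all three sequences. For men still in the extension at an interim analysis, use the data cutoff as the end date, as SAP 4.2.1 does for exposure.
- Apply the same definition to the extension-phase tables by concomitant medication use in SAP 8.1.6.
- State whether standard-of-care medicines appear in this summary or in a table of their own, and that the by-subject listing includes medicines started after the last study-drug dose.

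The cost is a few sentences and some reprogramming with dates the SAP already defines. No new data are needed. SAP section 1 already provides for recording changes made after finalization in the clinical study report.

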8.5. Electrocardiogram (ECG) Results

A shift table of the investigator's assessment of ECG results at baseline versus Week 13 or Early Termination from double-blind phase will be presented by double-blind treatment group for the Safety Analysis Set. The shift tables of ECG results for baseline vs. Extension Week 156 or Early Termination will be presented for subjects in the filgotinib 200 mg to open-label filgotinib 200 mg group for the Extension Phase Safety Analysis Set.

The investigator will rate the ECG based on the following categories: normal; abnormal (not clinically significant); abnormal (clinically significant); or missing. Baseline values will be ECGs collected with a nominal visit of "Screening"; Week 13 will include nominal visits of "Week 13" or "Early Termination" if early termed from double-blind phase; and Week 156/early termination will have nominal visits of "Extension Week 156" or "Early Termination" if early terminated from extension phase and taking open-label filgotinib.

The number and percentage of subjects in each cross-classification group of the shift table will be presented. Subjects with a missing value at baseline or postbaseline will not be included in the denominator for the percentage calculation. No formal statistical testing is planned.

A by-subject listing for ECG assessment results will be provided by subject ID number and visit in chronological order.

